Our goal is to perform a proof-of-concept preliminary study of ketamine in tinnitus associated with sensori-neural hearing loss. MRS imaging will be used to assess ketamine-induced changes in GABA in the auditory cortex.]

Specific Aims and Hypotheses

Concisely state the objectives of the study and the hypothesis or primary research question(s) being examined. There should be one hypothesis for every major study procedure or intervention. For pilot studies, it is important not to overstate the study's objectives. If there are no study hypotheses, describe broad study goals/aims.

Specific Aim 1: To test the effect of ketamine in subjects with tinnitus. We will use a randomized, cross-over design in 40 subjects. Each subject will receive ketamine (0.5 mg/kg IV) versus placebo. Subjects will serve as their own controls and the sessions will be performed in a controlled laboratory environment with experienced personnel. We will use the dose of ketamine that has been shown to be effective in depression and anxiety disorders (0.5 mg/kg), administered intravenously, to allow the delivery to be paced and carefully controlled. The outcome measures will include measures of tinnitus burden, depression and anxiety.

Specific Aim 2: To investigate changes in GABA in the auditory cortex before and after ketamine administration. An MRS imaging study has shown a decrease in GABA levels in the right auditory cortex in tinnitus subjects (Sedley et al., 2015). Our group has shown that ketamine (0.5 mg/kg IV) increases cortical GABA, measured with MRS, in subjects with obsessive compulsive disorder and depression (Rodriguez et al., 2015, Milak et al., 2016). Thus, our hypothesis is that ketamine will increase GABA levels in the auditory cortex, in subjects suffering with tinnitus. We will investigate the correlation between the change in GABA with symptom improvement.]

Protocol Summary Form

Description of Subject Population

In this section, you are to describe each subject population of the study. The demographics of the population should reflect the gender and ethnic distribution of each population being studied. Enter each subject population's sample size, Gender, Racial, and Ethnic breakdown, and finally, describe each subject population.

Example:

Sample subject population:

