The research team will review the imaging facility safety guidelines with the participant and answer any questions they may have. While at the imaging facility participants will be required to wear a mask not containing metal (KN-95) and gloves. The participant will be met in the lobby of the imaging facility by a single member of the research team, also wearing an MRI compatible mask and gloves, at this time their temperature will be checked to ensure they do not have a fever. Participants with normal temperatures will be escorted down to the scanner. The participant and the research team will wear metal-free masks throughout the interaction, from first physical contact between researcher and staff in the lobby to seeing the subject off in the lobby after the scan. If the researcher deems it appropriate, the participant may shift their mask to their chin while in the scanner.

Prior to ketamine or placebo administration, the subjects will be positioned in the MRI scanner. The MRS scans will be obtained with 0.5 mg/kg IV of ketamine hydrochloride in saline or saline alone, administered over 40 minutes. The MRS data frames will be acquired (as follows: one pre-ketamine, and 5 following the 40-minute ketamine infusion. Each scan session is up to 2 hours in time. A study physician (Drs. [name] or [name]) will be present during the ketamine and placebo infusions. The two scan sessions will occur on different days, separated by at least 14 days.

Vital signs will be constantly monitored prior to, during, and after the ketamine infusion until the end of the MRS scan. Blood pressure and heart rate will be monitored and recorded at baseline and at 5-minute intervals and throughout the ketamine infusion. After that, vital signs will be acquired every 10 minutes until at least 90 minutes have passed since the beginning of infusion. The ketamine will be stopped for systolic BP increases to > 180 mm Hg and remains > 180 mm Hg for more than 5 minutes, or diastolic BP increases to > 110 mm Hg and remains > 110 mm Hg for more than 5 minutes. Subjects will be asked to stay until: 1) at least 1 hour after the end of the MRS scan has passed, 2) there are two measurements at least 15 minutes apart that are within 10 mmHg of the baseline systolic and diastolic blood pressure; 3) the acute subjective effects of ketamine have subsided. They will be assessed by a study physician prior to being discharged home. Transportation home will be provided for using a car service.

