Briefly, a high-speed localizer imaging series will be obtained, followed by a volumetric T1-weighted spoiled gradient recalled echo scan. Brain spectra containing GABA and Glutamate/Glutamine (Glx) resonances will be acquired of the auditory cortex using the volume-selective PRESS J-editing difference method. Data will be acquired from a voxel oriented parallel to and placed superiorly abutting the Sylvian fissure and centered on Heschl's sulcus, encompassing most of Heschl's gyrus, including the primary auditory cortex, the planum temporale, the superior temporal sulcus,

Protocol Summary Form

planum polare, and small portions of the insula and middle temporal gyrus adjacent to these auditory regions. The GABA and Glx peak areas will be quantified as ratios relative to the area of the unsuppressed voxel tissue water.

Statistical Plan and Data Analysis:

Specific Aim 1: To test the effect of ketamine in subjects with chronic tinnitus induced by hearing loss. The primary clinical outcome measures will be the severity of tinnitus, which will be fitted with a mixed linear effects model, with each outcome modeled as a function of infusion type (active ketamine vs placebo), infusion order (ketamine first vs placebo first), baseline scores, and post-infusion time (day after infusion, vs week after infusion). The test of the hypothesis will be the main effect of infusion type, and for descriptive purposes the difference in post-infusion scores (and 95% confidence limits) between active ketamine and placebo will be calculated from the model.

Specific Aim 2: To investigate changes in GABA in the auditory cortex in tinnitus subjects, before and after ketamine administration.

The GABA/W values will be fitted using a mixed linear effects model, with infusion type (ketamine vs placebo), infusion order (ketamine first vs placebo first), and MRS data frame, as fixed effects, and subject and scan (nested within subject) as random effects. When the overall F test reaches significance ($p < 0.05$, 2-tailed) a post hoc analyses will be conducted to identify the potential effects of ketamine at each of the 6 MRS acquisitions. Analysis across the six 13-min acquisitions will give a more detailed picture of which time points are driving the trend. The effect of ketamine of Glx/W will be included as an exploratory analysis.

Criteria for Early Discontinuation

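### As listed, the Aim 2 GABA model treats the pre-infusion frame as an outcome rather than a baseline, and opens six unadjusted ketamine tests on an F test it does not name

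*Combined protocol and SAP*

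**What the plan says.** All references are to the combined protocol and SAP.

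- **Frames.** Under MRI scans and ketamine infusion (Study Procedures), each session collects "one pre-ketamine, and 5 following the 40-minute ketamine infusion". Ketamine and placebo sessions are at least 14 days apart.
- **Model.** Statistical Plan and Data Analysis, Specific Aim 2, fits the GABA/W values using "infusion type (ketamine vs placebo), infusion order (ketamine first vs placebo first), and MRS data frame, as fixed effects". The random part has a subject term and a term for each scan inside a subject. No baseline term and no infusion-by-frame term is listed. The Aim 1 model just above it does include baseline scores, and names the main effect of infusion type as its test.
- **Decision rule.** The post hoc step depends on an overall F at the two-sided 5% level. Once that gate is passed, the plan says that "a post hoc analyses will be conducted to identify the potential effects of ketamine at each of the 6 MRS acquisitions". Which F is meant is not stated, and no multiplicity adjustment is given.
- **Aim.** Specific Aims and Hypotheses words Aim 2 as "To investigate changes in GABA in the auditory cortex before and after ketamine administration", hypothesises a rise, and plans to correlate the change in GABA with symptom improvement.

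**The concern.** The first of the six frames precedes any drug, so it cannot carry a ketamine effect. Its natural use is as the baseline for that session. Three things follow from treating it as a sixth outcome.

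1. The infusion main effect averages the ketamine-placebo difference over six frames, one of which is zero in expectation. The estimate is smaller than the post-infusion effect of interest.
2. Differences between a subject's two sessions that affect every frame stay in the standard error. The pre-infusion frame measures that shift and could remove part of it.
3. The listed model gives the same ketamine-placebo difference at every frame. It cannot express a before-to-after change or show at which acquisitions the effect appears, yet the post hoc step asks for exactly that.

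The decision rule adds a separate problem. With the F unnamed and six tests unadjusted, the false-positive rate for frame-wise claims depends on a choice the plan leaves open. One of the six tests can only ever produce a false finding.

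**Working it through.** **Inputs from the documents.** Frames per session: 1 + 5 = 6, which agrees with the six acquisitions in the Aim 2 analysis text. Completers: 30 (Description of Subject Population); Aim 1 speaks of 40 subjects. I use n = 30. Significance level: 0.05, two-sided.

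**Inputs assumed.** The documents give no effect size, variance or power for Aim 2, so there is no planned figure to reproduce. I set the within-subject variance of one frame to 1 and let r be the share of it that is between scans, with equal correlation among frames of a scan. The ketamine effect d is constant over the five post-infusion frames unless stated otherwise.

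**1. Dilution.** Infusion main effect over six frames = (0 + 5d)/6 = 0.833d, an attenuation of 16.7%. This does not depend on r.

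**2. Information.** Variance of the per-subject ketamine-placebo difference:

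- as listed (mean of six frames): 2[r + (1-r)/6], effect 5/6
- five post frames with the pre frame as covariate: 2[r + (1-r)/5 - r²], effect 1

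Information is effect²/variance. The ratio is the equivalent gain in sample size.

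| r | Variance, as listed | Variance, adjusted | Information, as listed | Information, adjusted | Ratio |
|---|---|---|---|---|---|
| 0 | 0.333 | 0.400 | 2.083 | 2.500 | 1.2 |
| 0.2 | 0.667 | 0.640 | 1.042 | 1.563 | 1.5 |
| 0.5 | 1.167 | 0.700 | 0.595 | 1.429 | 2.4 |

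If the adjusted analysis had 80% power with 30 completers (an assumed anchor), the listed one would have about 73%, 63% and 44% (noncentral t).

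**3. Power at an assumed effect of 0.5 SD, n = 30.** The third column tests change from the pre-infusion frame, which is what adding an interaction alone would do; its variance is 2 × 1.2(1-r).

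| r | As listed (infusion main effect) | Change from pre frame | Five post frames, pre frame as covariate |
|---|---|---|---|
| 0 | 96.8% | 40.1% | 98.7% |
| 0.3 | 67.6% | 53.3% | 88.5% |
| 0.5 | 53.3% | 67.6% | 88.5% |
| 0.7 | 43.7% | 87.7% | 94.9% |

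The covariate analysis is best at every r. The interaction alone is worse than the current main effect when r is small.

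**4. False frame-wise findings.** Six independent tests at 0.05 would give 1 - 0.95⁶ = 26.5% with no gate. With the gate, the rate depends on which F is meant. Simulation used n = 30, r from 0 to 0.7, and paired t tests at 0.05 in each frame:

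| Scenario | Infusion-type F | Frame F | Whole-model F (approximate) |
|---|---|---|---|
| No ketamine effect; 0.5 SD drift after the pre frame, common to both infusions | 3-5% | 17-22% | 17-21% |
| True 1 SD effect in the first two post frames only; any of the four null frames declared | 6-15% | 13-18% | 13-18% |

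In the drift scenario the frame F opens the gate in 78% to 100% of runs. With a true 0.5 SD effect in all five post frames and an infusion-type gate, the pre-infusion frame is itself declared a ketamine effect in 2.6% to 4.6% of runs.

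**The case against.** **The overall F is probably the infusion main effect.** By parallel with Aim 1 this is the natural reading, and under it the error rate with no ketamine effect is held near 5%. A reader might infer from six unadjusted tests that type I error is uncontrolled, at 17-27%. The documents do not support that as a general statement: the gated rates of about 17-22% need a frame or whole-model F opened by drift. Nor can these rates be added to the 5/6 dilution, which needs the infusion-type F. What stands is that the F is unnamed, and that even the infusion-type gate does not protect null frames when the effect is real in others.

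**An interaction may be intended.** Asking for effects at each acquisition suggests so, and if the interaction were the tested F the 5/6 dilution would not apply. A reader might infer that the plan rejects an interaction; it simply does not list one. This is under-specification, and adding the term alone would not be a safe repair (step 3).

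**A chance pre-infusion difference is already allowed for.** A reader might infer that such a difference is counted as a drug effect and invalidates the test. It does not: the scan random effect puts session shifts into the standard error, so the cost is precision. GABA/W is also a ratio to voxel water, which may reduce some session variation; how much is unknown.

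**The variance share is assumed.** This is correct. The larger power losses depend on it, and the 5/6 factor assumes a constant post-infusion effect.

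**This is a proof-of-concept study with tests labelled post hoc.** That bears on severity. It does not explain leaving the available baseline unused.

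**Conclusion.** The concern holds as one of efficiency and specification. Under the natural reading of the F, the listed analysis targets 5/6 of a constant post-infusion effect and discards baseline information. The equivalent sample-size loss is a factor of 1.2 at r = 0, 1.5 at r = 0.2 and 2.4 at r = 0.5. The direction is the same at every r checked from 0 to 0.7; the size depends on r, which the documents do not give.

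Frame-wise error is near 5% with no ketamine effect under an infusion-type gate, and about 6-15% for null frames when the effect is confined to two post-infusion frames (an assumed scenario). It reaches about 17-22% with no ketamine effect only under a frame or whole-model F with common drift.

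A reader might also take this to be the trial's only mechanistic test. It is not: a correlation of GABA change with symptoms and an exploratory Glx/W analysis are planned. Since Aim 2 is a mechanistic aim of a proof-of-concept study, this should be fixed but is not a barrier to the trial.

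**What to change.** Amend the Aim 2 paragraph of the Statistical Plan:

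1. **Outcome and baseline.** Model the five post-infusion GABA/W frames. Enter each session's pre-infusion GABA/W as a covariate, split into the subject's mean over both sessions and the session's deviation from it.
2. **Terms.** Fixed effects: infusion type, frame, infusion-by-frame, order and period. Random effects: subject and scan within subject.
3. **Single test.** Name ketamine minus placebo, averaged over the five post-infusion frames, as the Aim 2 test at two-sided 5%. This replaces the overall F.
4. **Follow-up.** Only if that test is significant, test the five frame-specific contrasts with a multiplicity adjustment such as Holm.
5. **Pre-infusion difference.** Report it as a balance check only, not as a ketamine effect.

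A model constraining the two pre-infusion means to be equal would be a reasonable alternative to step 1. The cost is wording, one or two degrees of freedom in the within-subject comparison (baseline deviation and period), and no additional data. The change should be made before GABA results are examined by infusion.

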Subject Population	Number of completers required to accomplish study aims	Projected number of subjects who will be enrolled to obtain required number of completers	Age range of subject population
Participants with tinnitus	30	60	21-60

Suicide Risk Management Plan

This section will include all information regarding the Suicide Risk Management Plan.

[Any participant reporting suicidal ideation or behavior to any member of the research team will be evaluated. If the patient is an active suicide risk, 911 will be called and/or the participant will be escorted to the Emergency Department. If the participants is not an active risk, they will be provided with referrals for outpatient treatment. If the participant has outpatient treatment in place, their clinician will be notified.]

Recruitment Procedures

This section will include all information regarding your study's recruitment process/procedures.

Describe settings where recruitment will occur. [Subjects will be recruited through advertisements or word of mouth]

How and by whom will subjects be approached and/or recruited? [As above]

Clinical Trials:

Please provide the NCT Registration Number for your Clinical Trial. **NCT03336398**]

YOU MUST REGISTER AT [ClinicalTrials.gov](https://clinicaltrials.gov) IMMEDIATELY UPON RECEIPT OF IRB APPROVAL AND PRIOR TO ENROLLMENT OF THE FIRST SUBJECT. YOU WILL BE PROVIDED WITH A NCT REGISTRATION NUMBER ON REGISTRATION. PLEASE REVISE THIS SECTION OF THE PROTOCOL SUMMARY FORM TO INCLUDE THE NCT NUMBER AND RE-SUBMIT AS AN AMENDMENT TO THE IRB.

Protocol Summary Form

Concurrent Research Studies

In this section, please identify if subjects in this study participate in or will be recruited from other studies.

Describe where subjects are recruited from. [N/A]

Describe the recruitment source for (Must provide IRB Number, PI and Title). [N/A]

Inclusion/Exclusion Criteria

This section details your study sample(s) and addresses the requirement for risk minimization.

You may choose to divide your sample by population (healthy controls vs. patient population) or by procedure (subjects who will have an MRI vs. those who will not) and then define different sets of criteria for each.

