Screening will also include the following scales: The Tinnitus Functional Index (TFI): The TFI is a widely used and reliable self-administered test to determine the degree of functional impairment in tinnitus patients (Meikle *et al*, 2012). 2) The Tinnitus Handicap Inventory (THI), a widely used and reliable self-administered test to determine the degree of distress in tinnitus patients (Newman *et al.*, 1996). The THI consists of 25 questions that cover three domains: functional, emotional, and catastrophic; 3) Visual Analogue Scale (VAS), a straight line of 10 mm with no numbers other than 0 (no tinnitus) to 100 (maximal experience of tinnitus). The subject marks their level of tinnitus (loudness and annoyance) on the line, and the outcome is measured in millimeters; 4) The Beck Depression Inventory (BDI), a 21 question multiple choice inventory used to assess depressed mood, including irritability, physical symptoms of depressed mood, and

distress; 5) Profile of Mood States (POMS), is a questionnaire used to assess mood states, and includes scales that investigate depression/dejection, tension/anxiety, fatigue/inertia, confusion/bewilderment. 6) The Beck Anxiety Inventory (BAI), a 21-item self-report measure of anxiety. The scales will be obtained at screening, at the beginning and end of the ketamine/placebo sessions, and daily for 10 days after the sessions. As much as the screening procedures as possible will be acquired remotely via a HIPAA compliant method. The questionnaires will be completed via Qualtrics (remotely) prior to the in-person visit.

MRI scans and ketamine infusion:

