Define criteria that will be used to exit or drop subjects from the study and operationalize. Indicate the time points when such criteria will be applied, and describe the rating instruments, parameters, and thresholds that will lead to a decision to terminate a subject's participation and the role of the person who will make these determinations. Studies which include a medication taper and discontinuation may be asked to include an independent medical monitor (an MD not on the study team) who will aid the study team in determining whether study discontinuation is needed. In addition, explain procedures for managing subjects who are withdrawn from the protocol.

For treatment studies: To minimize risks to subjects, operationalized drop-out criteria should be defined so that subjects who worsen, or in some cases, fail to improve, are removed from the study and offered standard care. The threshold for drop-out should consider the level of risk associated with non-improvement for the specific disorder, the availability of alternatives, and the typical required duration of treatment. For example, emergence of suicidal intent, or psychosis, should prompt immediate clinical evaluation and withdrawal from the study.

Subjects will be withdrawn from the study if

Protocol Summary Form

1. They request it for any reason.
2. Systolic BP increases to > 180 mm Hg and remains > 180 mm Hg for more than 5 minutes, or diastolic BP increases to > 110 mm Hg and remains > 110 mm Hg for more than 5 minutes.
3. Negative subject response to ketamine, such as dysphoria, anxiety, paranoia, or any adverse event.
4. Subjects experience a worsening of depressive symptoms or an BDI > 31 and/or the participant is found to be at risk of suicide by the study clinician.
5. The PI judges that it is medically unwise to continue in the study, for example if the subjects are unable to comply with the study procedures and rules.]

Blood and other Biological Samples

Describe how the sample will be used and indicate, when relevant, the amount of the sample. The IRB wants to know that the sample is sufficient for the purposes of the study, but that sampling is limited to what is minimally necessary.

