Ketamine is an FDA-approved dissociative anesthetic. Ketamine exposure at the subanesthetic dose to be used in this study can be associated with a moderate dissociative state, which is well tolerated in the majority of cases. There is extensive clinical experience with ketamine used at anesthetic doses and no long-term detrimental effects of ketamine exposure have been reported. It is possible that ketamine administration will increase the risk of psychosis, even in normal subjects. Ketamine is a street drug of abuse, and thus poses the risk that exposure during this study may predispose subjects to subsequent abuse of this drug. For this reason, a history of any past or present problems with substance use will be obtained on screening; history of substance or alcohol dependence or diagnosis of abuse in the prior year will be exclusionary.

An increase in vital signs can also occur with the infusion of ketamine. Subjects will be closely monitored for changes in blood pressure or heart rate, and the infusion will be stopped if needed. As described above, the ketamine will be stopped for systolic BP increases to > 180 mm Hg and remains > 180 mm Hg for more than 5 minutes, or diastolic BP increases to > 110 mm Hg and remains > 110 mm Hg for more than 5 minutes. After the scan, the monitoring of subjects will continue and blood pressure will be obtained until there are two measurements at least 15 minutes apart that are within 10 mmHg of the baseline diastolic blood pressure. After the subject is transferred back to the examination room, the blood pressure and heart rate will be obtained manually by the research assistant or nurse.

Ketamine administration has the potential to produce agitation or hyperarousal. If needed, this will be treated with intravenous diazepam and the study terminated. The risks of exposing healthy subjects to a drug of abuse potential will be minimized by explaining this risk to prospective subjects, and by excluding from the study any subjects with documented or suspected prior substance or alcohol history of dependence or abuse as outlined in the inclusion/exclusion criteria.

2) MRI scanning: It may be uncomfortable to lie motionless in the scanner (MRI) and it may cause some subjects to feel anxious. While there have been no reports of any long-term effects caused by magnets of the same or even higher strength, the long-term effects of being placed in a magnet of this strength (3 Tesla) are unknown. The MRI scanner uses

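### Subjects who react badly to ketamine are withdrawn from the study with no planned outcome follow-up, so the Aim 1 estimate leans toward subjects who tolerate the drug

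*Combined protocol and SAP*

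**What the plan says.** All references are to the combined protocol and SAP.

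- **Criteria for Early Discontinuation.** The list opens "Subjects will be withdrawn from the study if". Criterion 3 is "Negative subject response to ketamine, such as dysphoria, anxiety, paranoia, or any adverse event", with no severity threshold. Criterion 2 is a systolic or diastolic rise above a limit for more than 5 minutes. Criterion 4 covers worsening depression, a BDI above 31 or suicide risk. The form's instruction in the same section asks the investigator to "explain procedures for managing subjects who are withdrawn from the protocol"; the answer lists five criteria and no follow-up.
- **Study Procedures.** For the same blood pressure limits this section says only "The ketamine will be stopped for systolic BP increases": the infusion ends, and leaving the study is not mentioned. The scales are taken at screening, at the start and end of each session, "and daily for 10 days after the sessions". Questionnaires are already completed remotely at screening.
- **Risks/Discomforts/Inconveniences, ketamine infusion.** On agitation or hyperarousal: "If needed, this will be treated with intravenous diazepam and the study terminated".
- **Statistical Plan and Data Analysis, Specific Aim 1.** A mixed linear model has terms for infusion type, infusion order, baseline score and "post-infusion time (day after infusion, vs week after infusion". The test is the main effect of infusion type. No analysis population, missing-data rule or sensitivity analysis is given.
- **Quality Assurance Monitoring Plan, B.7.** Monitors check that withdrawals are recorded and explained on the CRFs. That is not outcome follow-up.

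**The concern.** Withdrawal here happens after randomisation, and under criterion 3 a reaction to the active drug triggers it. The scores it removes are those the Aim 1 test uses. The loss is also uneven within the crossover: a placebo-first subject who reacts in the second session leaves placebo scores in the data and no ketamine scores, while a ketamine-first subject leaves neither, because the placebo session never takes place.

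A mixed model can use incomplete data, but it is unbiased only if missingness depends on data the model contains. The acute reaction is not in the model, and no later ketamine score exists to stand in for it. The model in effect assumes that reactors would have scored like those who stayed. The Background section describes anxiety and low mood as reinforcing tinnitus, so reactors might well have scored worse. The Aim 1 result would then describe subjects who tolerate ketamine while being read as the effect in everyone given it.

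**Working it through.** **What is lost, by timing**

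| Withdrawal | Day-after ketamine score | Week-after ketamine score | Placebo scores |
|---|---|---|---|
| In ketamine session, placebo first | lost | lost | kept |
| In ketamine session, ketamine first | lost | lost | never obtained |
| After day 1, before day 7, placebo first | kept | lost | kept |
| After day 1, before day 7, ketamine first | kept | lost | never obtained |

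**Size.** The plan has no power calculation, SD, effect size or withdrawal rate, so there is no figure of its own to reproduce. What follows is an illustration.

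Inputs:
- Dosed subjects N = 40, from Specific Aims and Hypotheses. (The Description of Subject Population gives 30 completers from 60 enrolled, so 30 is also tried.)
- Two-sided alpha 0.05. The plan states this for Aim 2 only; it is assumed for Aim 1.
- w = share withdrawn in the ketamine session. Assumed 5%, 10%, 20%.
- d = how much worse the ketamine-minus-placebo difference is in withdrawn than in retained subjects, in SDs of the paired difference. Assumed 0, 0.5, 1.0.
- True mean effect over all dosed subjects: zero.

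Formulas. If the retained subjects' mean is m, the withdrawn subjects' mean is m + d (higher is worse). The overall mean is (1 − w)m + w(m + d) = m + wd = 0, so m = −wd. The bias is therefore w × d in ketamine's favour. With n = N(1 − w) complete pairs, the chance of a significant result favouring ketamine is the upper tail of a noncentral t with n − 1 degrees of freedom and noncentrality wd√n, beyond the 97.5% point of t.

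Worked case, w = 10%, d = 1.0: 40 × 0.10 = 4 withdrawn, n = 36, bias 0.10 SD, noncentrality 0.10 × √36 = 0.60, critical value 2.030, chance 8.4%.

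| w | Withdrawn | Ketamine scores lost per scale (2 each) | d = 0 | d = 0.5 | d = 1.0 |
|---|---|---|---|---|---|
| 5% | 2 | 4 | 0 SD; 2.5% | 0.025 SD; 3.5% | 0.05 SD; 4.8% |
| 10% | 4 | 8 | 0 SD; 2.5% | 0.05 SD; 4.8% | 0.10 SD; 8.4% |
| 20% | 8 | 16 | 0 SD; 2.5% | 0.10 SD; 7.9% | 0.20 SD; 19.4% |

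With 30 dosed and d = 1.0, the chances are 7.2% at w = 10% and 15.4% at w = 20%.

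The paired test drops a placebo-first subject's lone placebo scores, whereas the planned model would keep them. A simulated random-intercept model with infusion, order and baseline, 40 subjects and d = 1.0 gave similar answers: bias 0.110 SD and 9.2% at w = 10% (2000 runs), 0.193 SD and 16.7% at w = 20% (700 runs). With both infusions' scores kept for withdrawn subjects, the bias was 0.02 SD or less in size, with chances of 3.0% and 2.0% (700 runs each). That is somewhat optimistic about any remedy, because a ketamine-first withdrawal would still have no placebo session.

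For scale, the 95% confidence half-width at 40 pairs is 2.023/√40 = 0.32 SD.

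**The case against.** The strongest reply is that the plan is silent rather than prohibitive: the daily schedule carries no exception for withdrawn subjects, and staff might collect the scales anyway. That is true, but the stated rule is removal from the study, and no section gives a basis for expecting scores afterwards.

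Other objections stand and limit the point.

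- **Direction.** A reader might infer that the plan biases Aim 1 toward ketamine. The documents do not establish this. The Background describes a cycle of tinnitus and distress; it does not say that dysphoria during a 40-minute infusion predicts tinnitus a day or a week later. Subjects also stay on site until acute effects subside. If reactors' later tinnitus is no worse, the bias is zero.
- **Opposing withdrawals.** Criteria 1, 4 and 5 can apply after placebo, and the adverse-event wording in criterion 3 can be read that way too. Criterion 4 withdrawals after placebo could remove poor placebo scores and push the other way. The table is not the net bias.
- **Replacement.** The population table's "Projected number of subjects who will be enrolled to obtain required number of completers" might suggest that reactors are replaced by subjects who tolerate ketamine. It does not say so, nor that analysis is limited to completers.
- **Size.** The protocol expects most people to tolerate the dissociative state, and expected dissociation need not trigger criterion 3. Eligibility excludes hypertension and most psychiatric illness. Withdrawals may be few. Against that, the adverse-event wording has no severity limit, so the text puts no ceiling on them.
- **Safety.** Removing a subject from further dosing is right. Continued questionnaires for someone at suicide risk are a clinical matter and should not be automatic.

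**Conclusion.** The point holds in a limited form. As written, the plan gives up Aim 1 ketamine scores because of a reaction to ketamine that the model does not contain, so the estimate leans toward subjects who tolerate the drug. Both time points are lost for a reaction in the session, and only the week-after score for one reported after day 1.

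Under the stated assumptions the bias ranges from nothing to 0.20 SD. The 19% figure needs both upper limits at once, and at 5% withdrawn the bias is small against a half-width of 0.32 SD. Size rests on an unknown withdrawal rate; size and direction both rest on an unmeasured difference between reactors and others. This should be changed because the remedy is cheap and scores not collected cannot be recovered, not because a false positive has been shown to be likely.

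**What to change.** 1. **Criteria for Early Discontinuation.** For criteria 2 and 3, replace withdrawal from the study with: no further infusion or scan, but the remote daily scales for the 10 days after the infusion already started are still collected unless the subject withdraws consent. For criterion 4, do the same only if the study clinician agrees it is appropriate, with referral to care first. Keep every stopping threshold, and align the agitation sentence in the Risks section.
2. **Statistical Plan, Specific Aim 1.** State that the analysis includes every randomised subject who starts an infusion, with all scores obtained, whether or not the infusion or second session was completed. Report withdrawals by criterion and by infusion.
3. **Optional.** Add a sensitivity analysis that shifts scores still missing toward worse values, with shifts chosen by the study team in advance.

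**Cost.** One amendment and revised consent wording; no new visits or instruments. Some subjects will decline. Scores after rescue diazepam reflect both drugs and must be flagged. Subjects withdrawn with ketamine first will still lack placebo scores, and scores of subjects already withdrawn cannot be recovered.
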